Diagnostic confidence for the evaluation of LVEF	
Diagnostic confidence for the evaluation of LVEF (LVEF will be calculated using the formula: (end diastole volume – end systole volume)/end diastole volume) will be scored for non-contrast and OPTISON-enhanced echocardiographic acquisitions separately using the following scale:
 
0 = no confidence 1 = low confidence 2 = moderate confidence 3 = high confidence
 
And the change in diagnostic confidence will be derived by comparing non-contrast and OPTISON-enhanced diagnostic confidence scores as follows (contrast-enhanced minus unenhanced):
 
≤ -1 = confidence is lower with contrast-enhanced images 0 = confidence is the same between unenhanced and contrast-enhanced images 1 = confidence is slightly improved with contrast-enhanced images 2 = confidence is moderately improved with contrast-enhanced images 3 = confidence is greatly improved with contrast-enhanced images

The suitable dosage of OPTISON for CE-ECHO in pediatric patients will be primarily determined by the improvement in the number of segments adequately visualized over non-contrast images, supplemented by LVO peak contrast intensity assessed as medium or better, peak LV contrast filling to around 67% or better, and duration of contrast enhancement to ≥ 1.5 minutes. Image quality and diagnostic confidence, as well as overall safety of OPTISON in the pediatric population, will also be taken into consideration for the dose selection.

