12.3.4 Reader Differences

Summaries of the image readings by reader will be presented.

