6.4 Efficacy Analysis

6.4.1 General Considerations

Since this is a dose-finding study, no hypotheses are being tested. All efficacy results will be summarized for the FAS and PP populations.

Assessments to be used for image interpretation are identified by the site and recorded in the eCRF. These identified assessments will be used for efficacy analyses.

Efficacy summaries will be presented for each reader.

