6.4.2 Primary Efficacy Analysis

Visualization of the 12 segments of the left ventricle wall in standard apical 4-chamber and 2-chamber views will be measured by the qualitative EBD visualization scale:

0 = no visualization of the LV endocardial border

1 = poor visualization

2 = fair visualization

3 = good/optimal visualization

Results for each segment will be summarized for non-contrast and OPTISON dose levels overall and by weight group ($\leq 40, > 40$ kg). A category “Visualized”, corresponding to scores 2 or 3, will also be presented. Additionally, the number of segments visualized (segments rated as “fair visualization” or “good/optimal visualization”) will be derived from the EBD score and summarized for non-contrast and OPTISON dose levels, overall and by weight group. 95% CI will be presented. A Paired t-test will be used to compare the number of segments visualized between non-contrast and each OPTISON dose level.

The number and percentage of subjects with an increase in the number of segments adequately visualized over non-contrast images will also be tabulated overall and by weight group for each OPTISON dose levels.

The Total LV EBD score, calculated as the sum of the individual scores assigned to each of the segment (range 0 to 36), will be tabulated overall and by weight group for non-contrast and each OPTISON dose level. The change from non-contrast to each OPTISON dose level will also be presented. 95% CI will be presented. A Paired t-test will be used to compare Total LV EBD scores between non-contrast and each OPTISON dose level.

A suboptimal echocardiogram is defined as ≥ 2 contiguous segments in any given view that cannot be visualized. The number and percentage of subjects with suboptimal echocardiogram will be presented for non-contrast and each OPTISON dose level, overall and by weight group.

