6.4.3 Secondary Efficacy Analyses

The following secondary endpoints will be summarized, overall and by weight group ($\leq 40, > 40$ kg):

- The LV peak contrast intensity, determined as None, Low, Medium, High or Blooming, will be summarized as a categorical variable for each OPTISON dose level.

- The peak LV contrast filling, categorized as None (0% filling), Faint (around 33% filling), Intermediate (around 67% filling) or Full (100% filling), will be summarized as a categorical variable for each OPTISON dose level.
- The contrast enhancement duration in the LV chamber determined from the time contrast appears in the LV to the time it almost dissipates from the chamber as determined by investigators, will be summarized with descriptive statistics for each OPTISON dose level.
- Image quality, categorized as Excellent/good, Adequate or Poor will be summarized as a categorical variable for each OPTISON dose levels.
- Diagnostic usefulness, evaluated as Non-diagnostic (the image quality is not sufficient to confidently visualize the endocardial border) or Diagnostic (sufficient or excellent image quality for EBD assessments), will be summarized as a categorical variable for non-contrast and OPTISON dose levels.
- The diagnostic confidence of the assessment of LV EBD and wall motion, assessed using a 4-point scale (0 = no confidence, 1 = low confidence, 2 = moderate confidence, 3 = high confidence) will be described for non-contrast and OPTISON dose levels.

The change in diagnostic confidence will be derived by comparing non-contrast and OPTISON-enhanced diagnostic confidence scores as follows (contrast-enhanced minus unenhanced):

- ≤ -1 = confidence is lower with contrast-enhanced images
- 0 = confidence is the same between unenhanced and contrast-enhanced images
- 1 = confidence is slightly improved with contrast-enhanced images
- 2 = confidence is moderately improved with contrast-enhanced images
- 3 = confidence is greatly improved with contrast-enhanced images.

Diagnostic confidence in comparison to non-contrast echocardiographic images will be summarized as a categorical variable by OPTISON dose level.

- The diagnostic confidence of the evaluation of LVEF, assessed using a 4-point scale (0 = no confidence, 1 = low confidence, 2 = moderate confidence, 3 = high confidence) will be described for non-contrast and OPTISON dose levels.

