The change in diagnostic confidence will be derived using the same method as for change diagnostic confidence of the assessment of LV EBD and wall motion and summarized as a categorical variable by OPTISON dose level.

- LV function assessed by LVEFs, calculated using the formula: (end diastolic volume – end systolic volume)/end diastolic volume for each ventricle, will be summarized with descriptive statistics for non-contrast and OPTISON dose levels
- A composite assessment of dose suitability will be made at the subject level and results will be tabulated by OPTISON dose level. A dose will be considered suitable if it meets the following criteria:
 - (1) There is an increase in the number of segments adequately visualized over non-contrast images
 - (2) LVO peak contrast intensity assessed as medium or better
 - (3) Peak LV contrast filling to around 67% or better
 - (4) Duration of contrast enhancement ≥ 1.5 minutes.

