6.4.5 Reader Differences

All efficacy summaries described in Section 6.4 will be presented by reader.

Data from re-read will be listed.

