8 LIST OF TABLES, FIGURES AND DATA LISTINGS THAT ARE TO BE PROGRAMMED

Whenever applicable, tables listed below will present results overall and by weight group and will be repeated by reader.

TABLE NUMBER	TABLE TITLE	POPULATION FOR ANALYSIS
14.1.1	Summary of Subject Disposition	All Subjects
14.1.2.x	Summary of Subject Demographics	Safety, FAS, PP
14.1.3	Summary of Medical History	Safety
14.1.4.1	Summary of Prior Medications	Safety
14.1.4.2	Summary of Concomitant Medications	Safety
14.1.5	Summary of Exposure to OPTISON	Safety
14.2.1.1a	Summary of Visualization of LV Wall by Segments	ITT
14.2.1.1b	Summary of Visualization of LV Wall by Segments	PP
14.2.1.2a	Summary of Visualization of LV Wall Overall	ITT
14.2.1.2b	Summary of Visualization of LV Wall Overall	PP
14.2.2a	Summary of Peak Contrast Intensity in LV	ITT
14.2.2b	Summary of Peak Contrast Intensity in LV	PP
14.2.3a	Summary of Peak Contrast Filling in LV	ITT
14.2.3b	Summary of Peak Contrast Filling in LV	PP
14.2.4a	Summary of Contrast Enhancement Duration in LV	ITT
14.2.4b	Summary of Contrast Enhancement Duration in LV	PP
14.2.5a	Summary of Image Quality	ITT
14.2.5b	Summary of Image Quality	PP

TABLE NUMBER	TABLE TITLE	POPULATION FOR ANALYSIS
14.2.6a	Summary of Diagnostic Usefulness	ITT
14.2.6b	Summary of Diagnostic Usefulness	PP
14.2.7a	Summary of Diagnostic Confidence of LV EBD and Wall Motion Between Contrast and Non-Contrast Enhanced Images	ITT
14.2.7b	Summary of Diagnostic Confidence of LV EBD and Wall Motion Between Contrast and Non-Contrast Enhanced Images	PP
14.2.8a	Summary of Diagnostic Confidence of LVEF Between Contrast and Non-Contrast Enhanced Images	ITT
14.2.8b	Summary of Diagnostic Confidence of LVEF Between Contrast and Non-Contrast Enhanced Images	PP
14.2.9a	Summary of LV Function Assessed by LVEF	ITT
14.2.9b	Summary of LV Function Assessed by LVEF	PP
14.2.10a	Summary of Dose Suitability	ITT
14.2.10b	Summary of Dose Suitability	PP
14.3.1	Overall summary of Treatment Emergent Adverse Events	Safety
14.3.1.1	Summary of Treatment Emergent Adverse Events by System Organ Class and Preferred Term	Safety
14.3.1.2	Summary of Treatment Emergent Adverse Events by maximum severity by System Organ Class and Preferred Term	Safety
14.3.1.3	Summary of Treatment Emergent Adverse Events considered related to IMP by System Organ Class, Preferred Term	Safety
14.3.2.1	Summary of Serious Treatment Emergent Adverse Events by System Organ Class and Preferred Term	Safety

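### Reader-scored efficacy results are specified only reader by reader, so the segment count that mainly drives dosage has three results per dose and no combined one; it is also unclear who measures contrast duration.

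*SAP*

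**What the plan says.** **Handling of the three reads.** SAP 2.5 and Protocol 8.3 assign three independent blinded readers, who do not see dosing information. Four places say what is done with their scores:

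- Protocol 12.3.4: "Summaries of the image readings by reader will be presented".
- SAP 6.4.1: "Efficacy summaries will be presented for each reader".
- SAP 6.4.5: "All efficacy summaries described in Section 6.4 will be presented by reader". Re-read data are listed only.
- SAP Section 8: "Whenever applicable, tables listed below will present results overall and by weight group and will be repeated by reader".

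In the SAP, overall is set against weight group. It means all weights together, not all readers together. Neither document states a mean, majority, consensus, adjudication or lead-reader rule.

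**What depends on the reads.** Protocol 10.2.1 says the suitable dosage is "primarily determined by the improvement in the number of segments adequately visualized over non-contrast images", supplemented by other image measures, with safety also considered. SAP 6.4.2 gives the segment count a 95% CI and a paired t-test of each dose level against non-contrast. For the total LV EBD score it adds "The change from non-contrast to each OPTISON dose level will also be presented"; it does not list that output for the segment count. SAP 6.4.3 adds: "A composite assessment of dose suitability will be made at the subject level and results will be tabulated by OPTISON dose level".

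**Who measures duration.** SAP 6.4.3 defines duration from the time "contrast appears in the LV to the time it almost dissipates from the chamber as determined by investigators", and Protocol 12.3.2 also names investigators. SAP 2.2 lists duration among the echocardiographic analyses done under the Independent Review Charter. The Protocol synopsis bases the efficacy assessment on the blinded image evaluation.

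**The concern.** The primary objective is to find a suitable dosage, and one measure is named as its main determinant. With by-reader output alone, that measure has three results at each dose level, none of them designated as the summary value. Each result carries the full scoring noise of one reader, although two further reads of the same images already exist. With 30 evaluable subjects, that precision is worth having.

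The duration conflict affects the composite directly. If investigators time the contrast, criterion 4 has one value per subject and dose, shared by all three reader-specific verdicts, and it comes from staff who know the dose. If blinded readers time it, criterion 4 can differ by reader and is scored without dosing information. A programmer could not derive the composite from the SAP without guessing which applies.

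**Working it through.** **1. The plan's own figure.** The only calculation in the documents is the power table for duration (SAP 2.3, Protocol 12.5): paired t-test, one-sided alpha 0.025, mean difference 0.7 minutes, SD 1.5 minutes. The noncentral t with n − 1 degrees of freedom and noncentrality (0.7/1.5) × √n gives 69.5%, 82.1%, 89.9%, 94.5%, 97.1% and 98.5% for n = 30, 40, 50, 60, 70 and 80. The table's 70, 82, 90, 94, 97 and 98% reproduce. The table involves no reader rule, so it neither supports nor weakens this point.

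**2. Inputs for the precision check.**

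- From the documents: 3 readers (SAP 2.5) and N = 30 evaluable subjects (SAP 2.3).
- Assumed: an inter-reader correlation r of the change from non-contrast of 0.4, 0.6 or 0.8; a single-reader SD of that change of 2, 3 or 4 segments; equal SDs across readers.

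**3. Variance of the three-reader mean relative to one reader:** r + (1 − r)/3.

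| r | Variance ratio | SE lower by | Single-reader N with equal precision (30/ratio) |
|---|---|---|---|
| 0.4 | 0.600 | 22.5% | 50.0 |
| 0.6 | 0.733 | 14.4% | 40.9 |
| 0.8 | 0.867 | 6.9% | 34.6 |

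**4. 95% CI half-width for the mean change in segments.** For one reader it is t(0.975, 29) × SD/√30, with t = 2.045. For the mean of three, multiply by the square root of the variance ratio.

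| SD | One reader | Mean, r = 0.4 | r = 0.6 | r = 0.8 |
|---|---|---|---|---|
| 2 | 0.75 | 0.58 | 0.64 | 0.70 |
| 3 | 1.12 | 0.87 | 0.96 | 1.04 |
| 4 | 1.49 | 1.16 | 1.28 | 1.39 |

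**5. Spread among the three reader-specific means.** With no systematic reader bias, the expected gap between the highest and lowest is 1.69 × SD × √((1 − r)/30). At SD 3 this is 0.72, 0.59 or 0.41 segments for r = 0.4, 0.6 or 0.8. In simulation, readers differ on the sign of the change in under 1% of trials when the true change is 0.5 SD. The issue is the size and precision of the estimate, not its direction.

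**6. Composite, illustration only.** Assume a latent-normal model, between-dose subject correlation 0.5, all four criteria reader-specific, and suitability of 50% at one dose and 60% at the other. At least two readers then rank the doses in opposite directions in about 22–37% of trials. Most of this is sampling noise at N = 30: a single reader misranks the doses in about 13–16% of trials and a 2-of-3 rule in about 9–13%. At 50% against 70%, opposite rankings fall to 4–9%.

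**The case against.** The case against is substantial. By-reader output is stated consistently in the SAP. No hypotheses are formally tested, the dose choice weighs several inputs, and neither document requires one headline number. Because SAP 6.4.5 covers everything in Section 6.4, the composite can be read as one verdict per reader, subject and dose. The Independent Review Charter, not supplied, may set a combination or adjudication rule. Every input to the precision gain beyond the number of readers and N is assumed.

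Most of this stands, and it limits the point. A reader might infer that the analysis is undefined or invalid; it is not, since by-reader summaries are a usable plan. A reader might infer that the sponsor could quietly choose a favourable reader. The documents do not support that: all three sets of tables are to be shown, and SAP Section 9 requires departures from the SAP to be described with reasons in the study report. A reader might take the opposite-ranking figures as evidence that readers will conflict over the dose. They rest wholly on assumed inputs and mostly reflect the small sample.

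Two things remain. If all three reads are present for every subject, the combined estimate is simply the average of the three reader means, but its confidence interval needs per-subject averages, which the planned summary tables do not provide. And the conflict over who measures duration lies in the documents' text; it does not depend on the charter's reading rules or on any assumption.

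**Conclusion.** The point holds as an improvement to a sound descriptive plan, together with one inconsistency to resolve. Adding a three-reader mean would lower the standard error of the segment-count change by roughly 7–22% for inter-reader correlations of 0.8 down to 0.4, at no cost in patients or reads. That range depends on assumed correlations and equal reader SDs; the half-widths also depend on the assumed SD.

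A 2-of-3 rule for the composite is not needed. No precision gain is claimed for it, and it can contradict the reader mean on criterion 1: changes of +1, +1 and −3 segments give a majority for an increase but a mean of −0.33.

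The disagreement over the source of duration should be settled before the composite is derived. Confidence is medium, mainly because the charter was not available.

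**What to change.** 1. In SAP 6.4.1–6.4.2, add the per-subject mean of the three readers for number of segments visualized and total LV EBD score as the pre-specified summary value. Report the change from non-contrast with its 95% CI at each dose level for both. If the charter already sets a combination rule, cite it instead.
2. In the FAS, apply SAP 6.4.4 to each read before averaging. One zero-scored read pulls the mean down (8, 8 and 0 segments give 16/3 = 5.3), so add a sensitivity analysis restricted to interpretable reads.
3. Keep all by-reader tables. A combined value can mask reader differences, and these tables show them.
4. Reconcile SAP 6.4.3 and Protocol 12.3.2 with SAP 2.2 and the Protocol synopsis on whose duration measurement enters the composite.
5. Keep the composite by reader. A 2-of-3 summary is optional and supportive only.

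The cost is SAP wording and modest programming, plus a matching clarification of the Protocol wording if it is to agree. No new reads, readers or patients are needed.

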6.4.2 Primary Efficacy Analysis

Visualization of the 12 segments of the left ventricle wall in standard apical 4-chamber and 2-chamber views will be measured by the qualitative EBD visualization scale:

0 = no visualization of the LV endocardial border

1 = poor visualization

2 = fair visualization

3 = good/optimal visualization

Results for each segment will be summarized for non-contrast and OPTISON dose levels overall and by weight group ($\leq 40, > 40$ kg). A category “Visualized”, corresponding to scores 2 or 3, will also be presented. Additionally, the number of segments visualized (segments rated as “fair visualization” or “good/optimal visualization”) will be derived from the EBD score and summarized for non-contrast and OPTISON dose levels, overall and by weight group. 95% CI will be presented. A Paired t-test will be used to compare the number of segments visualized between non-contrast and each OPTISON dose level.

The number and percentage of subjects with an increase in the number of segments adequately visualized over non-contrast images will also be tabulated overall and by weight group for each OPTISON dose levels.

The Total LV EBD score, calculated as the sum of the individual scores assigned to each of the segment (range 0 to 36), will be tabulated overall and by weight group for non-contrast and each OPTISON dose level. The change from non-contrast to each OPTISON dose level will also be presented. 95% CI will be presented. A Paired t-test will be used to compare Total LV EBD scores between non-contrast and each OPTISON dose level.

A suboptimal echocardiogram is defined as ≥ 2 contiguous segments in any given view that cannot be visualized. The number and percentage of subjects with suboptimal echocardiogram will be presented for non-contrast and each OPTISON dose level, overall and by weight group.

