6.2.1 Justification of Dose Selection and Efficacy Analysis

In the adult controlled clinical trials for the LVO and EBD indication, the duration of the useful imaging time for LV chamber opacification was 2.5 to 4.5 minutes for a dose of 0.5 to 3.0 mL [OPTISON PI].

McMahon et al conducted rest non-contrast and CE-ECHO in 20 children (9 to 18 years) with limited transthoracic echo windows [McMahon et al. 2005]. OPTISON was administered at a dose of 0.3 mL per injection for children <20 kg and 0.5 mL per injection for those ≥ 20 kg. The EBD was significantly improved in all patients with CE-ECHO and LVEF was measurable in all 20 patients using contrast echo versus only 11 with non-contrast echocardiography. Zilberman et al performed contrast stress echocardiography with OPTISON administration in 22 children (8 months to 19 years; mean age 9.3 ± 3.9 years) [Zilberman et al. 2003]. A dose of 0.1 mL was given for patients ≤ 25 kg, and 0.2 mL for patients > 25 kg. These doses provided adequate opacification of the LV cavity for up to 60 seconds.

Similar to the two publications, OPTISON dose in this study will be administered based on body weight. According to the Centers for Disease Control and Prevention Pediatric Growth Charts [CDC Growth Charts], children > 9 years of age usually weigh > 28 kg and children > 12 years of age usually weigh > 40 kg for both boys and girls in the United States, but weight varies greatly for a specific age. Two dose levels will be tested in each weight cohort: 0.1 or 0.2 mL per injection to children weighing ≥ 20 to ≤ 28 kg, 0.2 or 0.3 mL per injection to those who weigh > 28 to ≤ 40 kg, and 0.2 or 0.4 mL per injection to those who weigh > 40 kg. It is expected that one or more of these dose levels will be able to provide adequate LVO and EBD in these groups of pediatric patients with a limited transthoracic echocardiographic window.

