2.2 Study Design

This is a Phase 4, open-label, non-randomized, multi-center, multi-dose study in North America and Europe. The study is designed to evaluate overall efficacy and safety of intravenous administration of OPTISON at various doses in pediatric patients undergoing transthoracic echocardiography.

Approximately 50 pediatric patients between ≥ 9 and <18 years of age weighing ≥ 20 kg who are clinically indicated for a transthoracic echocardiogram and are likely to have a limited transthoracic echocardiographic window based on body habitus and/or previous cardiac operation or have a previous suboptimal non-contrast echo cardiogram will be enrolled into the study. Per FDA Advice/information request dated 2023, February 16th, a reduction of the sample size to 30 evaluable subjects was agreed.

OPTISON will be administered according to pediatric body weight (≥ 20 to ≤ 28 kg, >28 to ≤ 40 kg, and >40 kg). Each patient will receive administrations of 2 different dose levels. Up to 3 injections per dose level are allowed to be administered if significant technical issue(s) have occurred e.g., patient related needs, scanner malfunction, or drug injection error, with the total injected dose not to exceed the value defined in Table 1. Injections should be at least 10 minutes apart between the 2 dose levels to allow for clearance of the previous dose.

Table 1 OPTISON Dosing Table

Body weight (kg)	Dose/injection (mL) Dose level 1	Dose/injection (mL) Dose level 2	Total dose (mL) not to exceed (3 injections/dose level)
≥ 20 to ≤ 28	0.1	0.2	1.0
>28 to ≤ 40	0.2	0.3	1.5
>40	0.2	0.4	1.8

[figure not shown]
For echocardiographic imaging, standard apical 4-chamber and 2-chamber views will be obtained at baseline using tissue harmonic imaging, thereafter with contrast using a contrast-imaging mode. Additional views may be obtained at the clinician's discretion. All image views will be obtained prior to and after contrast administration until 10 minutes post injection. All images will be recorded on disk and sent to sponsor's image core lab for preparation of blinded image evaluation (BIE).

Efficacy of echocardiographic images will be evaluated by independent blinded readers based on characteristics of left ventricular opacification (LVO), diagnostic confidence of LV EBD and wall motion, and diagnostic confidence of LVEF. Echocardiographic Analyses as per independent review charter includes:

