6 STATISTICAL ANALYSES

6.1 Demographics, Baseline Characteristics, Medical History, and Prior/Concomitant Medications

6.1.1 Demographic and Baseline Characteristics

Age (years between birth and time informed consent form was signed), sex, race, ethnicity, and baseline height, weight, weight group (≥ 20 to ≤ 28 , > 28 to ≤ 40 , > 40 kg; as well as ≤ 40 , > 40 kg), and body mass index (BMI) will be summarized overall, independent of IMP assignment, based on Safety, FAS, and PP populations.

Categorical data (sex, weight group, race, and ethnicity) will be summarized using frequencies and percentages. The number of subjects with missing information will also be summarized.

Continuous data (age, baseline height, weight and BMI) will be summarized with the number of non-missing observations by mean, standard deviation, median, Q1, Q3, minimum and maximum values.

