6.3 Study Drug Exposure and Compliance

The total treatment exposure (OPTISON injection in mL as well as number of administrations) received at two dose levels will be summarized by descriptive statistics overall and by weight group (≤ 40 , > 40 kg) based on Safety population. A summary of each subject's dosing information will be presented in a listing. The injection used for image interpretation will be identified in this listing. Reasons why OPTISON dose was repeated will also be listed.

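### Three weight bands are dosed differently, but efficacy is tabulated only overall and for ≤40 vs >40 kg, so neither dosing regimen below 40 kg gets its own results row

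*SAP*

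**What the plan says.** SAP 2.2 says that "OPTISON will be administered according to pediatric body weight", and its Table 1 sets three bands, each with two volumes per injection. Protocol 6.2.1 describes the same structure by cohort: "Two dose levels will be tested in each weight cohort: 0.1 or 0.2 mL per injection to children weighing" 20 to 28 kg, with a different pair for each heavier band.

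The outcome tables use a coarser split.

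- Primary endpoint (SAP 6.4.2): "Results for each segment will be summarized for non-contrast and OPTISON dose levels overall and by weight group", with the groups given as ≤40 and >40 kg.
- Secondary endpoints (SAP 6.4.3): "The following secondary endpoints will be summarized, overall and by weight group", with the same two groups.
- Suitability composite (SAP 6.4.3, in the same list): "A composite assessment of dose suitability will be made at the subject level and results will be tabulated by OPTISON dose level". Its weight split comes only from the lead-in sentence of that section.
- Exposure (SAP 6.3): volume and number of administrations "received at two dose levels will be summarized by descriptive statistics overall and by weight group", again ≤40 and >40 kg.
- Table list (SAP 8): where applicable, "tables listed below will present results overall and by weight group and will be repeated by reader". SAP 9 gives weight group as ≤40, >40 kg.

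The three bands appear in one summary only, the baseline characteristics of SAP 6.1.1: "weight group (≥ 20 to ≤ 28 , > 28 to ≤ 40 , > 40 kg; as well as" the two-group version. That table counts children per band and carries no outcomes.

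**The concern.** The primary objective in both documents is to determine a suitable dosage, and in this trial a dosage is a volume pair tied to a weight band. Two of the three regimens have no outcome row of their own. In the ≤40 kg rows, 0.2 mL is the high dose for the lighter children and the low dose for the heavier ones, so level 1 and level 2 do not each name one treatment. In the overall rows, level 2 combines 0.2, 0.3 and 0.4 mL. Only the >40 kg stratum has one volume per level.

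A pooled ≤40 kg figure is a weighted average whose weights are the numbers enrolled in each band. Nothing fixes those numbers. Protocol Amendment A01 removed the minimum of 10 per weight group, and the SAP reduces the target to 30 evaluable subjects. The same band results could therefore give different pooled figures. A band summary assembled from listings after the data are seen would not be prespecified.

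**Working it through.** **The plan's own figure.** SAP Table 3 gives paired t-test power for a 0.7-minute difference, SD 1.5, one-sided 0.025. With the noncentral t distribution (df = n − 1, noncentrality (0.7/1.5)√n), power at n = 30, 40, 50, 60, 70 and 80 is 69.5%, 82.1%, 89.9%, 94.5%, 97.1% and 98.5%. The plan states 70, 82, 90, 94, 97 and 98%, so the table reproduces. This point does not depend on it.

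**What each row pools.** Volumes are from SAP Table 1. Dose level is read as level 1 or level 2, as in that table.

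| Row | Level 1 (mL) | Level 2 (mL) |
|---|---|---|
| Overall | 0.1, 0.2 | 0.2, 0.3, 0.4 |
| ≤40 kg | 0.1, 0.2 | 0.2, 0.3 |
| >40 kg | 0.2 | 0.4 |

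If the rows were built by mL instead, the 0.1 and 0.3 mL rows within ≤40 kg would each come from one band. The 0.2 mL row would still mix both, so neither band's full result would be shown.

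**Does weight scaling make the two lower bands alike?** Volume divided by weight at the band edges, in microL/kg:

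- Level 1: 0.1 mL at 28 to 20 kg gives 3.57 to 5.00; 0.2 mL at 40 to 28 kg gives 5.00 to 7.14. The ranges meet only at 5.00, so overlap over joint span is 0/3.57 = 0%.
- Level 2: 0.2 mL at 28 to 20 kg gives 7.14 to 10.00; 0.3 mL at 40 to 28 kg gives 7.50 to 10.71. Overlap is (10.00 − 7.50)/(10.71 − 7.14) = 2.50/3.57 = 70%.

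Pooling is therefore mainly a problem at level 1.

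**Sensitivity to mix.** Let d be the difference between the two lower bands in the share suitable at level 1. If the lowest band's share of the ≤40 kg children moves from w1 to w2, the pooled share moves by d × (w2 − w1). Neither document gives d or the band sizes; both are assumed here, with 12 children ≤40 kg.

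| Split, lowest : middle band | Multiplier | d = 10 points | d = 20 points | d = 40 points |
|---|---|---|---|---|
| 2:10 to 10:2 | 10/12 − 2/12 = 0.667 | 6.7 | 13.3 | 26.7 |
| 1:11 to 4:8 | 4/12 − 1/12 = 0.25 | 2.5 | 5 | 10 |

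As an illustration, take 40% suitable in the lowest band and 80% in the middle band. The pooled figure is 72%, 60% or 48% when the lowest band makes up 20%, 50% or 80% of the stratum. None of these is the result for either regimen.

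**Precision of a band table.** The 95% CI half-width for a mean is t(0.975, n − 1)/√n in SD units: 2.48 at n = 3, 1.24 at n = 5 and 0.84 at n = 8. Exact 95% intervals for a share near 80% are 28.4–99.5% for 4/5 and 44.4–97.5% for 8/10. Power for the 0.7-minute difference within a band is 13% at n = 5 and 26% at n = 10. Band tables can only be descriptive.

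**The case against.** The strongest objection concerns size. Protocol 6.2.1 expects children over 9 years usually to weigh more than 28 kg, and entry starts at 9, so a stratum dominated by the lowest band is unlikely. Over the 1:11 to 4:8 range the shift is 2.5, 5 or 10 points, well below the wider range. This stands, and the top of the wider range should be read as an outer bound. It does not support pooling, however: if the lowest band is nearly empty, the ≤40 kg row mostly describes the middle band while appearing to cover the 0.1/0.2 mL regimen.

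Second, no hypotheses are tested and the composite has fixed criteria, so a count by band leaves little analytic freedom, and listings of exposure, segments and suitability are planned. That weakens the prespecification argument but does not remove it, because a listing is not a summary.

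Third, the protocol asks only for separation by dose level; the SAP's two groups are finer than that and are disclosed in SAP 9. Both are true. SAP 9 gives no reason for the 40 kg cut, though small bands may explain it.

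Fourth, the documents never use volume per kg as an analysis measure, and on that measure the >40 kg stratum, which has no upper weight limit, is heterogeneous too. That is fair, but that stratum is still a single regimen as planned.

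Finally, small cells may add little beyond the listing. That is a real cost, and a reason to show n and omit tests.

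**Conclusion.** The concern holds. As written, no planned summary shows efficacy, enhancement duration, suitability or exposure for the 20–28 kg or >28–40 kg regimens separately, and dosage by weight band is what the primary objective is about. This is a gap in reporting, not an error of calculation, and it does not invalidate the planned tables. The problem is concentrated at level 1, where the per-kg ranges of the two lower bands do not overlap; at level 2 they share 70% of the joint span. The effect of mix on the pooled figure cannot be fixed from the documents. Under the assumed 12 children and a 20-point difference between bands it is 5 to 13 points, depending on how far the split can vary. The change should be made, but it is not critical.

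**What to change.** In SAP 6.4.2, 6.4.3 and the table list (14.2.1.1, 14.2.1.2, 14.2.4 and 14.2.10), add descriptive tables of the primary endpoint, enhancement duration and suitability composite by the three Table 1 bands. Label columns by mL per injection, show n in each band, and state that the tables are descriptive, with no tests. Present the exposure table (14.1.5) the same way. Use the three-band variable already defined in SAP 6.1.1. Keep the overall and ≤40/>40 kg summaries as supportive, and give the reason for the 40 kg cut in SAP 9.

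The cost is SAP wording and programming, with no new data and no change to conduct. Four tables in two populations for three readers make 4 × 2 × 3 = 24 outputs to extend, plus 14.1.5. The drawback is sparse cells, which the displayed n makes plain.
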